3.7.4 Power and sample size

3.7.4.1 Power analysis

A power analysis was conducted to determine appropriate sample size for the study to detect a statistical difference between change scores for the primary hypothesis in a two tailed, repeated measures t-test. Assuming that our samples are independent and identically distributed with normal distribution (see [3.7.3](#)), we analyse the required sample size as follows:

- We conduct sample size analysis using G*Power 3.1.9.7
- We use a two-tailed t-test.
- Cohen (1988) suggests a small effect size is 0.20 and medium effect size is 0.50. As a point of comparison, a meta-analysis of internet-based treatments for adult depression have reached an average effect size of 0.41 (Anderson & Cuijpers, 2009). Meanwhile, Motter et al. (2016) found in their meta-analysis that computerised cognitive training had an effect size of 0.43 on depression symptom severity. Thus, we use an effect size $d = 0.40$.
- We use an alpha error probability of 0.0167 that corresponds to an alpha level of 0.05 with Bonferroni correction for the three primary endpoint tests.
- We use power of 0.80
- We allocate subjects equally to the three arms, leading to allocation ratio of 1:1:1

This leads to a total sample size of 133 per arm and with three arms this equals 399 subjects, which we round to **400 subjects** that we aim to have in T3.

Karyotaki et al. (2015) explored the dropout in self-guided web-based interventions for depression using different psychotherapeutic approaches. While their approach is based on psychotherapies, and ours on cognitive training, the medium of training is the same

(web-based), the intervention is self-guided, and they target people with depression. Karyotaki et al. found that in 10 RCTs 59% of the subjects dropped out before completing half the treatment modules.

Meanwhile, Torous et al. (2020) explored dropout rates for app interventions for depression. Considering publication bias, they found a dropout rate of 47.8%.

Considering the above, we assume a dropout rate of 50%. Thus, we aim to recruit up to 400 subjects / 0.50 = 800 subjects to begin the study.

3.7.4.2 Recruitment and investigation termination condition

Once we have 133 subjects in each of the three research arms that fulfil the data analysis criteria as explained in [3.7.2](#), we will close the recruitment for the study. The subjects who are already recruited at this moment will carry on with the intervention. We will consider the gathered sample complete when these subjects have completed their intervention period up to time T3. When no subjects remain in either intervention or follow-up periods, we will terminate the investigation.

3.7.5 Interim analysis

Interim analysis in clinical trials is an analysis, and hence unblinding, of partially acquired data, which is conducted before the data collection has been completed. This can be performed to assess whether the investigational device can be proven to be (i) clearly beneficial or (ii) harmful compared to the comparator, or to be (iii) obviously futile.

We will use a pre-defined and pre-programmed interim analysis to assess these three conditions and thereafter infer whether the investigation should be stopped early or if the investigation plan warrants a change in terms of the to-be acquired cohort size. If evidence for one alternative is acquired, such modifications allow the saving of resources and subjects' efforts.

The interim analysis will be conducted when each arm has 33 or more subjects that have completed the 12 first weeks of the investigation and meet the inclusion criterion to data analysis (see [3.7.2](#)).

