3.3.1.2 Anticipated AEs

In guidelines for good clinical practice E6(R2) European medicines agency defines adverse events (AE) as: *“Any untoward medical occurrence in a patient or clinical investigation subject administered a pharmaceutical product and which does not necessarily have a causal relationship with this treatment.”*

The subjects may have unanticipated or anticipated adverse events during the study. Below, we have identified anticipated AE that may arise in the use of the MEL-T01 or MEL-S01 software. The list is based on possible negative events that may occur from playing entertainment video games (see Playstation, 2022) that closely resemble the MEL-T01 and MEL-S01 software. The adverse events are:

- Frustration
- Boredom
- Stress
- Eye ache
- Headache
- Dizziness
- Nausea
- Neck pain

- Visual disturbances
- Migraine
- Muscle twitching
- Uncomfortable feelings or ache in hands
- Losing sense of time and space

We take measures to mitigate the anticipated AE. We guide the user to pay attention to ergonomics, ensure sufficient lighting, and keep breaks while playing. Should the user encounter any AE, they are guided to stop playing, and report the AE to the researchers either through the in-game link or email. The information to the subjects is included in Appendix 2 (Tutkittavan tiedote) and the information given to the subject is found in Appendix 6 (Investigator's brochure). For AE reporting procedures, see [3.14](#).

Another risk is the potential addiction that video games may create. To mitigate this risk, we take the following precautions: 1) Digital game addiction is an exclusion criteria for the study. 2) We only recommend playing 45 minutes per day, and the players cannot play the game for more than 90 minutes per day at which point the game locks them out. 3) Our game doesn't include highly addictive features such as so-called loot boxes.

"A very small percentage of individuals may experience epileptic seizures or blackouts when exposed to certain light patterns or flashing lights." (Playstation, 2022). Considering the risk for epileptic seizure, we exclude subjects who have a history of epilepsy from the study to mitigate the risk. We also inform the subject about this (see Appendix 6 - Investigators brochure, 2.2.5.).

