3.6.3.4 Discontinuation criteria

The coordinating investigator may discontinue the study for the subject if

- Subject has an adverse event (AE) related to the device use
- Subject violates the Appendix 3 (Confidentiality obligation and right of use)
- Subject’s mental health deteriorates in a way that they are not fit for continuing in the study. This includes, for instance, psychotic symptoms, hospitalisation, and suicidality.

If the subject has a serious adverse event (SAE) their participation in the study is discontinued. For more information on the protocol regarding adverse events and serious adverse events, see section 3.14.5.

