3.7.2 Data-analysis-inclusion criteria and handling of missing data

To be included in the analysis of the primary hypothesis, the subject has to

- Have played the game version A or B at least 24 hours (50% of the recommended 48 hour game time) during the 12 weeks.
- The subjects must have answered all of the PHQ-9 items on both T0 and T2 or T3.

Handling of missing data:

- Primary endpoint evaluation will be based on the comparison of scores acquired ~~at~~ between T0 and T3.
- When the subject has played the MEL-T01 or MEL-S01 for 24 hours, but the T3 PHQ-9 score is missing, we will use the T2 PHQ-9 score.
- If the subject has accumulated ≥ 24 hours of intervention use and then ceased the use, we will use the first PHQ-9 score after the cessation of use.
- Subjects that do not meet these criteria are excluded from the analysis.
- In regards to our secondary hypotheses, missing data are handled similarly.

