3.7.5.2 Criteria for “harmful”

We will consider the digital interventions (MEL-T01 or MEL-S01) to be harmful if TAU is superior to either intervention so that:

The reduction in PHQ-9 score from T0 to T3 is

greater for TAU than for MEL-T01

OR

greater for TAU than for MEL-S01.

If either of the superiority conditions are met in a one-tailed t-test (or in a one-tailed Wilcoxon test if the conditions defined in [3.7.3](#) for using a parametric test are not met) with a Bonferroni-corrected ($N_{\text{tests}} = 2$) alpha-level of 0.0125, we consider the digital intervention as harmful to the subjects and terminate the investigation immediately.

Here, it is important to note that, at the discretion of the investigators, it is also possible to halt or terminate the investigation on the basis of harmfulness also at times other than that of the Interim analysis. As described in [3.15.2.2](#), evidence for such harmfulness could be excessive AEs in many subjects or an SAE that is related to the investigational device and may potentially be experienced by other than the subject first reporting it.

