3.15.2.2 Halt or termination of the investigation for all subjects

By design, the investigation will continue until the termination condition (see [3.7.4.2](#)) is met unless the results of the interim analysis lead to an earlier termination (see [3.7.5](#)). In addition to these termination conditions, we consider the following adverse-event-related conditions.

If MEL-S01 or MEL-T01 is deemed to be a probable or definitive cause for an SAE that another subject may face as well, or to cause unduly AEs in a larger subset of subjects, the whole study may be halted or terminated early to protect other subjects. Halting is warranted if a specific correctable device deficiency can be identified as the cause and in this case the halt continues until said deficiency is patched and validated to be corrected. If no such identification or correction is possible, the trial will be terminated. The decision is made by the principal investigator without delay upon communication from the coordinating investigator.

An early termination of the investigation may also be triggered if the Interim analysis identifies the intervention to be harmful (see [3.7.5.2](#)) or at the time of the Interim analysis, the investigators find the investigation to be futile (see [3.7.5.3](#)).

If such a decision is made, all the subjects are informed of the reasons for the study to be halted or terminated prematurely, and their access to the software is denied. The subjects are followed-up to evaluate the impact of the device on them leading to a full, written investigative report delivered to the relevant regulatory bodies.

The investigation may also be prematurely ended either immediately or by cessation of recruitment if the Interim Analysis indicates a high probability of MEL-T01 or MEL-S01 causing harm to the subjects.

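### The interim PHQ-9 harm rule leaves out device subjects who stop before 24 hours of play, so it is biased toward missing harm

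*Combined protocol and SAP*

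**What the plan says.** **Population.** Section 3.7.5: "The interim analysis will be conducted when each arm has 33 or more subjects" who have "completed the 12 first weeks of the investigation and meet the inclusion criterion to data analysis". That criterion is in 3.7.2. The first condition is "Have played the game version A or B at least 24 hours" within the 12 weeks. The second reads: "The subjects must have answered all of the PHQ-9 items on both T0 and T2 or T3". Anyone failing either condition is left out. A subject who reaches 24 hours and then stops is kept, with the first PHQ-9 after stopping.

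**Harm rule.** Section 3.7.5.2 compares PHQ-9 reduction from T0 to T3. It fires if TAU does better than MEL-T01, or better than MEL-S01, in a one-tailed test at 0.0125. It sets no population of its own. If it fires, "we consider the digital intervention as harmful to the subjects and terminate the investigation immediately".

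**Routes out of the device or the study.** Section 3.3.1.2: "Should the user encounter any AE, they are guided to stop playing". Section 3.6.3.4: "If the subject has a serious adverse event (SAE) their participation in the study is discontinued". The same section lets the coordinating investigator discontinue a subject whose mental health deteriorates.

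**Action after a harm signal.** Section 3.15.2.2 says that an interim harm finding may end the investigation "either immediately or by cessation of recruitment".

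**The concern.** A harm test should see the people who got worse. Here, a device subject whose depression worsens and who stops playing early is dropped before the comparison is made. Early stopping is not a marginal event: section 3.7.4.1 plans for 50% dropout, and the AE guidance and discontinuation criteria make stopping an expected response to trouble.

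The filter also falls on one side only. Table 6 in 3.11.1 gives the TAU arm no device access until after T3. Read literally, the 24-hour condition would exclude every TAU subject and the interim could never be triggered. The workable reading compares device subjects selected on play with TAU subjects who are not.

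What is at stake is the plan's only pre-specified PHQ-9 harm test. If it stays silent because the harmed have left it, recruitment continues.

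**Working it through.** **1. The plan's own figures.** With d = 0.40, two-sided alpha 0.0167 and power 0.80 (3.7.4.1), the two-sample t-test needs 133 per arm (power 0.803). This matches the plan, and 400 / 0.50 = 800 also matches. The harm alpha is 0.025 / 2 = 0.0125. The plan states no detection rate for the harm rule, so there is none to reproduce.

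**2. Harm rule with no selection.** The noncentrality is d × √(n/2) for n per arm. At d = 0.40:
- n = 33: 0.40 × √16.5 = 1.62, detection 0.26 per comparison.
- n = 66: 0.40 × √33 = 2.30, detection 0.51.
- No harm: 0.0125 per comparison. By simulation, about 0.023 that at least one of the two fires.

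**3. Harm concentrated in part of the arm.** Assumptions, not document figures: SD = 1; 50% of a device arm reaches 24 hours (33 of 66 randomised); 40% of device subjects are harmed by 1 SD; a share s of the harmed stops before 24 hours. The harmed share among qualifiers is 0.40 × (1 − s) / 0.50. There were 40,000 simulated trials per row, with a one-sided t-test at 0.0125, per comparison.

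| s | Harmed among qualifiers | Fires, 24-hour set (33 v 33) | Fires, all randomised (66 v 66) |
|---|---|---|---|
| 50% | 0.40 | 23% | 46% |
| 70% | 0.24 | 9% | 46% |
| 90% | 0.08 | 3% | 46% |
| 100% | 0 | 1% | 47% |

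In the first row stopping is unrelated to harm, since half of the harmed and half of everyone stop. The step from 23% to 46% in that row is therefore sample size alone. The fall from 23% to 9%, 3% and 1% down the third column is selection at a fixed sample size.

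**4. Uniform harm, stopping related to outcome.** Every device subject is harmed by 0.40 SD, and stopping correlates with a poor outcome at 0.2, 0.4 or 0.6 (assumed). Detection at 33 v 33 falls from 0.26 to 0.10, 0.03 and 0.007. With no harm and a correlation of 0.2, the rule fires 0.2% of the time, below its own alpha.

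**5. How far the gain depends on stoppers answering.** Suppose the non-qualifying half worsens by 0.5, 0.8, 1.0 or 1.2 SD and the qualifiers are unaffected.
- 24-hour set, 33 v 33: about 1.2-1.3% throughout.
- All randomised, 66 v 66, every stopper answers: 20%, 47%, 68% and 84%. Average harm is 0.5 × 0.5 = 0.25 SD up to 0.5 × 1.2 = 0.60 SD.
- Half of the stoppers answer (33 + 16 = 49 v 66): 8%, 17%, 26% and 37%. Average observed harm is 16/49 × 0.5 = 0.16 SD up to 16/49 × 1.2 = 0.39 SD.
- All randomised but held at 33 v 33: 9%, 21%, 32% and 45%.

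**The case against.** Four points on the other side carry weight.

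**Other harm routes exist and have no play-time filter.** Section 3.7.5.2 itself, and 3.15.2.2, allow a halt on AEs or an SAE at any time. SAEs go to the coordinating investigator at once (3.14.1), suicidal ideation triggers contact (3.6.3.5), and scheduled calls take place at weeks 4, 8 and 12. A reader might infer that the trial has no protection for early stoppers; the documents do not support that. These routes do not, however, compare PHQ-9 by arm. Worsening depression is not on the anticipated-AE list. Under 3.6.4.3 the coordinators see suicidality answers but no other questionnaire replies, and the other investigators' study-monitoring access covers play time, completion status and arm.

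**Later stoppers are kept.** A reader might infer that only those who go on playing are analysed. In fact 24 hours is a running total. It takes 24 / 1.5 = 16 days at the daily cap, or 24 / 4 = 6 weeks at the recommended pace, and 3.7.2 retains anyone who stops afterwards. The gap concerns stopping before 24 hours.

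**The AE guidance can be over-read.** It covers events such as headache and boredom, and does not say that stopping is permanent.

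**Detection need not collapse to alpha.** The 1% result requires all the harm to sit in early stoppers and the remaining players to match TAU. Nothing in the documents says so.

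It is also fair that part of the apparent gain from using all randomised subjects is sample size, and that dropouts may not answer. Both points reduce the size of the gain, not the direction of the bias.

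**Conclusion.** The point holds as a bias of unknown size. As written, 3.7.2, 3.7.5 and 3.7.5.2 together remove device subjects who stop before 24 hours from the only pre-specified PHQ-9 harm test. When stopping goes with worsening, that lowers the chance of detecting harm. On the assumptions shown, and at the same 33 per arm, detection falls from 23% to 9%, 3% or 1% as the share of the harmed who stop early rises from 50% to 70%, 90% or 100%. If stopping is unrelated to harm, there is no selection bias, only a smaller sample. The harmed fraction, the correlations and the response rate among stoppers are illustrative. The 50% reaching 24 hours borrows the plan's dropout assumption.

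It would go too far to say that the rule fires at its alpha whatever the harm, or that using all randomised subjects would secure 20-84% detection. The second range assumes that every stopper answers and twice the sample; it falls to about 8-37% if half of them answer.

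Separately, 3.7.5.2 prescribes immediate termination, while 3.15.2.2 makes ending discretionary and allows two forms of it. A pre-programmed rule needs one stated consequence, so the passages must be reconciled.

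**What to change.** - **3.7.5.2:** run the harm comparison on all randomised subjects due for T3 at the interim date, in the arm assigned, using every observed PHQ-9 after T0 and no minimum play time. State explicitly how TAU subjects qualify.
- **Interim report:** tabulate stopping before 24 hours, with reasons, by arm.
- **Questionnaires:** state that the online T1-T4 questionnaires continue to be requested from subjects who stop using the device, unless consent is withdrawn. This changes data collection only, not who is discontinued under 3.6.3.4 or 3.15.2.1.
- **3.7.5.2 and 3.15.2.2:** reconcile the action after a harm signal.

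**Cost.** Protocol and SAP wording, plus a change to the pre-programmed interim analysis. The questionnaires are already online, emailed and followed up by phone after seven days (3.10.1). The drawback is that off-device scores enter the harm test and would dilute a harm confined to continued use. The benefit also depends on how many stoppers answer.

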3.7.5.1 Criteria for “clearly beneficial”

We will consider MEL-T01 to be clearly beneficial if it reaches the primary endpoint so that:

The reduction in PHQ-9 score from T0 to T3 is

greater for MEL-T01 than for TAU

AND

greater for MEL-T01 than for MEL-S01.

If both superiority conditions are met in a one-tailed t-test (or in a one-tailed Wilcoxon test if the conditions defined in [3.7.3](#) for using a parametric test are not met) with an alpha-level of 0.025, the recruitment will be carried on until the next 33 data-analysis-qualified subjects have

been recruited to each of the three arms. After this recruitment goal has been achieved, the investigation will be terminated with the same process that is defined for the main termination condition (defined in [3.7.4.2](#)).

Thus, if evidence for MEL-T01 being clearly beneficial is observed, we will acquire a replication cohort to corroborate this observation and terminate the study.

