3.7.3 Hypothesis tests and multiple comparisons

Primary and secondary objectives in this clinical study are to demonstrate a statistical difference on outcome measure mean change scores between the following groups:

1. MEL-T01 and MEL-S01
2. MEL-T01 and TAU
3. MEL-S01 and TAU

We will first assess whether we use a parametric or non-parametric test.

- Using the Shapiro-Wilk test we explore if MEL-T01, MEL-S01, and TAU model residuals are normally distributed regarding PHQ-9.
- Using Levene's test we test whether the variance of MEL-T01, MEL-S01 and TAU model residuals are equal regarding PHQ-9.
- If both tests are $p > 0.05$, we will use a repeated measures Linear Mixed Model; If either test is $p < 0.05$, we will use a repeated measures Linear Mixed Model with robust standard errors.
- For primary endpoint evaluation (PHQ-9), we will conduct a one-tailed test for the arm pairs MEL-T01-vs.-MEL-S01, MEL-T01-vs.-TAU, and MEL-S01-vs.-TAU. We

are using a significance level of 0.05. Using Holm-Bonferroni correction, we find the multiple-comparison corrected $p = 0.05/3 = 0.0167$.

Change scores are defined as the scores obtained between the pre-intervention (T0) assessment and the during/post-intervention assessments. The general formulation of the null and alternative hypotheses are

$$H_0: \mu_x = \mu_y$$

$$H_1: \mu_x \neq \mu_y$$

where H_0 is the null hypothesis, H_1 is the alternative hypothesis and $x, y \in \{A, B, TAU\}$, $x \neq y$.

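### The interim benefit rule in 3.7.5.1 adjusts no alpha and does not say which data and level decide the trial afterwards, so the 0.05 level can be exceeded and MEL-S01 vs TAU loses power on the early path

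*Combined protocol and SAP*

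**What the plan says.** Section 3.7.5 sets the timing: "The interim analysis will be conducted when each arm has 33 or more subjects" that have completed 12 weeks and meet the analysis criteria. Section 3.7.5.1 calls MEL-T01 clearly beneficial, and equates this with reaching the primary endpoint, when MEL-T01 beats TAU and also beats MEL-S01. The rule reads "If both superiority conditions are met in a one-tailed t-test" (or a Wilcoxon test) "with an alpha-level of 0.025, the recruitment will be carried on until the next 33 data-analysis-qualified subjects" have been recruited to each arm. The section explains: "we will acquire a replication cohort to corroborate this observation and terminate the study".

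The unshortened trial closes recruitment on a different count: "Once we have 133 subjects in each of the three research arms" meet the analysis criteria. At that point "The subjects who are already recruited at this moment will carry on with the intervention", and 3.7.5.1 adopts the same closing process.

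For the final primary tests, section 3.7.3 specifies three one-tailed contrasts at 0.05: "Using Holm-Bonferroni correction, we find the multiple-comparison corrected" level of 0.0167. The same section writes a two-sided alternative. Section 3.7.4.1 sizes the trial with a two-tailed test at 0.0167 and d = 0.40: "We use power of 0.80".

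MEL-S01 vs TAU is one of the three primary hypotheses (3.5) but is not part of the benefit rule. The harm rule in 3.7.5.2 corrects for its two tests (0.0125 each). Nothing adjusts the benefit look or the final level for having looked.

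**The concern.** A benefit look at a quarter of the data gives one more chance to succeed by luck. Unless the interim or the final level is tightened, the overall error rises above the stated level. How far depends on what the trigger means, and 3.7.5.1 points two ways: it speaks of reaching the primary endpoint, and also of a second cohort that is to corroborate the finding. The last analysis after a trigger (pooled data or new cohort, and at what alpha) is not described.

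The trigger also halves the trial for all three primary hypotheses although it tests only two. It fires more readily when the MEL-S01 sample happens to do badly, and that same sample then has to carry MEL-S01 vs TAU. If the cohorts are pooled, the data that caused the stop are used again, so the second 33 are not an independent replication and the estimated MEL-T01 effect is biased upward.

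**Working it through.** **Inputs.** Look at 33 per arm, one-tailed 0.025 on each of two contrasts, both required (3.7.5, 3.7.5.1). Then 33 more. Full size 133 (3.7.4.2). Holm from 0.05, one-tailed (3.7.3). d = 0.40, two-tailed 0.0167, power 0.80 (3.7.4.1). True effects below are assumptions, in SD units.

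**1. The plan's own figure.** For two arms of n, power is the upper tail of a noncentral t with 2n − 2 df and noncentrality d√(n/2), beyond the critical t. At n = 133: 0.40 × √66.5 = 3.26, giving 80.3% at two-sided 0.0167. The stated 133 per arm reproduces.

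**2. Information.** 33/133 = 24.8% at the look; (33 + 33)/133 = 49.6% after a trigger.

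**3. Size of effect that triggers.** t(0.975, 64 df) × √(2/33) = 1.998 × 0.246 = 0.49 SD on each contrast.

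**4. Power per contrast at d = 0.40.** Noncentrality is 0.40 × √33 = 2.30 at 66 per arm and 0.40 × √16.5 = 1.62 at 33.

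| n per arm | two-sided 0.0167 | one-sided 0.0167 | one-sided 0.05 (last Holm step) |
|---|---|---|---|
| 133 | 80% | 87% | 95% |
| 66 | 45% | 56% | 74% |
| 33 (new cohort alone) | 21% | 30% | 49% |

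These are unconditional. Given that the trigger fired, with true MEL-T01 = 0.8 and MEL-S01 = 0.4 over TAU, MEL-S01 vs TAU at 66 per arm has 43% power at one-sided 0.0167 (32% two-sided).

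**5. MEL-T01 vs MEL-S01 error.** Three arms of normal means were simulated at 33, 66 and 133 per arm, with one-sided Holm steps 0.05/3, 0.025 and 0.05. The devices are equal to each other and both 0.4–0.8 better than TAU. At least one million trials were run per scenario, and repeat runs agree to about 0.1 percentage point.

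| What decides after a trigger | Error under Holm | Error against a fixed 0.0167 |
|---|---|---|
| No look, all go to 133 | 4.2–5.0% | 1.67% |
| Pooled 66 per arm | 4.5–5.5% | 1.9–2.0% |
| The trigger is itself a claim | 5.7–6.7% | 3.4–3.8% |
| New 33 per arm alone | 3.7–4.4% | 1.4% |

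With no true difference between any arms, the error against the fixed 0.0167 is about 2% even if the trigger is a claim.

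**6. Estimate after a trigger.** If the true MEL-T01 minus MEL-S01 difference is 0.20 (with MEL-T01 0.40 over TAU), the mean pooled estimate is about 0.41. That implies a first-cohort mean of 2 × 0.41 − 0.20 = 0.62. If the truth is zero, the mean pooled estimate is about 0.29.

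**7. How often the rule fires.** About 9% of trials if MEL-T01 and MEL-S01 are 0.40 and 0.20 over TAU; about 36% if they are 0.80 and 0.40.

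**8. A strict bound.** With one-sided p < 0.001 on both contrasts, the Holm error in step 5 is at most 5.0%, even if the trigger is counted as a claim.

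The simulation uses known variance. It ignores the harm and futility rules and stands in for the mixed model of 3.7.3.

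**The case against.** The strongest defence has five parts.

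- **Holm.** 0.0167 is only the first Holm step. When both devices truly beat TAU, MEL-T01 vs MEL-S01 is usually tested at 0.05, so a reader who sets 3.4–3.8% against 1.67% and infers a doubled error rate is using the wrong baseline. This stands. Under Holm the worst reading gives about 1.35 times (6.7/5.0). It is still above 0.05.
- **Corroboration.** The plan intends further evidence after the trigger. If the new 33 must succeed alone, the error is not inflated. This stands too, but that test has only 30% power at one-sided 0.0167, and the plan does not say that it is the test.
- **66 is a floor.** The look is at 33 or more, and subjects already recruited carry on. True, and the documents give no figure for the overrun.
- **The early path is not the whole trial.** With MEL-S01 0.40 better than TAU, overall MEL-S01 vs TAU power under one-sided Holm falls only from 93% to 89% (MEL-T01 = 0.60) or from 95% to 84% (MEL-T01 = 0.80). This is fair context. It does not restore the stated power for a trial that has stopped early.
- **0.025 is not itself an outlandish bound.** A constant boundary with looks at 33 and 133 and overall one-sided 0.05 would allow 0.0276 at each look. This stands: the fault is that the final level is left unadjusted. A reader might infer that 0.025 lies outside any standard boundary, and that is not supported.

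**Conclusion.** The concern holds in a limited form and should be fixed. As written, the benefit look is unadjusted, and the data and alpha that decide the trial after it are unspecified. On the pooled or the claim reading, MEL-T01 vs MEL-S01 error can reach 5.5% or 6.7% against a stated 5%. On the new-cohort reading the error is held, at the price of very low power. This rests on one-tailed Holm as in 3.7.3 and on both devices being truly equal and 0.4–0.8 SD better than TAU. At 0.4 SD the pooled reading stays below 5%.

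The 80% power in 3.7.4.1 does not apply to MEL-S01 vs TAU after a trigger. The 45% figure belongs to the two-tailed basis of 3.7.4.1 and should not be quoted without 56%, the one-tailed first-step figure; the last Holm step gives 74%. The conflict between the one-tailed test in 3.7.3 and the two-tailed calculation in 3.7.4.1 is the source of this spread.

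A reader might also conclude that all early stopping for benefit has to go. The documents do not require that: 3.7.5 gives saving resources and subjects' effort as the purpose of the look, and removing it is a preference.

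**What to change.** In 3.7.5.1, replace 0.025 with a strict bound, for example Haybittle–Peto with one-sided p < 0.001 on both contrasts. Keep recruiting to 133 per arm for the primary tests, or at least for MEL-S01 vs TAU.

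If early curtailment is kept, the section should:
- state that the trigger is not itself an efficacy claim;
- state, for each primary hypothesis, which data and which interim-adjusted alpha decide it;
- restate power for the early path;
- drop the word replication if the cohorts are pooled, and note that the pooled estimate is biased upward.

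Reconcile the one-tailed tests in 3.7.3 with the two-sided alternative there and the two-tailed calculation in 3.7.4.1. The documents do not say whether the look has already taken place. If it has, record what it showed and fix the deciding data and alpha before the final analysis.

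The cost is wording, plus a smaller chance of an early saving, or none for any contrast that runs to 133. The present rule fires in about 9% (0.40 and 0.20 over TAU) or 36% (0.80 and 0.40) of trials. Under p < 0.001, the MEL-T01 vs MEL-S01 test alone caps this. The cap is P(Z > 3.09 − 0.20 × √16.5) = P(Z > 2.28), about 1%, in the first case, and P(Z > 3.09 − 0.40 × √16.5) = P(Z > 1.47), about 7%, in the second.

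### The replication cohort recruited after a positive interim has no analysis of its own, and nothing keeps the interim subjects out of the test meant to confirm them

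*Combined protocol and SAP*

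**What the plan says.** Section 3.7.5: "The interim analysis will be conducted when each arm has 33 or more subjects" who have finished the first 12 weeks and meet 3.7.2.

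Section 3.7.5.1 needs MEL-T01 to beat TAU and also MEL-S01 on PHQ-9 change. "If both superiority conditions are met in a one-tailed t-test" (Wilcoxon as the alternative), each at 0.025, "the recruitment will be carried on until the next 33 data-analysis-qualified subjects have" joined each arm. The stated purpose is replication: "we will acquire a replication cohort to corroborate this observation and terminate the study". After that, "the investigation will be terminated with the same process that is defined for the main termination condition".

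That process is 3.7.4.2. Recruitment closes and those already enrolled carry on. "We will consider the gathered sample complete when these subjects have completed their intervention period up to time T3".

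The only final analysis is in 3.7.3: a mixed model with one-tailed tests of three arm pairs and Holm-Bonferroni starting at 0.05/3 = 0.0167. Its population comes from 3.7.2: "To be included in the analysis of the primary hypothesis, the subject has to" have at least 24 hours of play and complete PHQ-9 data at T0 and at T2 or T3. Neither section mentions whether a subject was in the interim dataset.

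**The concern.** The second cohort exists to guard against a chance interim finding. It can do that only if its analysis is fixed in advance and does not reuse the data that prompted it. With nothing specified, the general analysis rules apply and take in all qualifying subjects, about 66 per arm, half of them already known to be positive. Agreement is then partly built in, and the estimated difference is too large.

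The choice between a pooled and a new-subjects-only analysis would also be made after the interim unblinding. The most exposed contrast is MEL-T01 versus MEL-S01, which section 3.6.2 relies on for its inference about cognitive training. A reader told that the result was replicated could be misled about both its certainty and its size.

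**Working it through.** **Inputs from the plan.** 33 per arm at the interim; both contrasts at one-tailed 0.025 (3.7.5, 3.7.5.1). 33 more per arm (3.7.5.1). Final one-tailed alpha 0.0167 (3.7.3). d = 0.40 (3.7.4.1). The plan gives no SD, so effects are in SD units.

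**Plan's own figure.** Two-tailed two-sample t-test, d = 0.40, alpha 0.0167, power 0.80: the noncentral t gives 132.2, rounded up to 133 per arm. This reproduces 3.7.4.1.

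**Single contrast, no true effect.** Interim and pooled Z statistics have correlation √(33/66) = 0.707. P(pooled Z > 2.128 given interim Z > 1.96) = 26%. For independent new subjects it would be 1.67%.

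**Three arms, both-contrast interim rule.** Simulated t-tests, 33+33 per arm, conditional on a positive interim. T01, S01 and TAU denote the arms.

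| True T01−TAU, T01−S01 | Trials entering the path | Pooled T01 vs S01 passes | New subjects alone | Mean pooled T01−S01 |
|---|---|---|---|---|
| 0, 0 | 0.46% | 29% | about 1.6% | 0.30 |
| 0.40, 0 | 2% | 26% | about 1.7% | 0.29 |
| 0.40, 0.20 | 8.6% | 60% | 9% | 0.41 |
| 0.80, 0.40 | 35% | 87% | 30% | 0.53 |

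With no device effect, both pooled contrasts pass at 0.0167 in 14% of cases (20% with full Holm step-down) and at least one passes in 44%. With equal games, Holm step-down raises the false T01 over S01 confirmation to 38–39%.

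**Why the estimate is biased.** It averages a selected half and an unselected half. With equal games, the interim T01−S01 difference averages 0.58 among positive interims, so (0.58 + 0)/2 = 0.29. At a true 0.20 it averages 0.616, so (0.616 + 0.20)/2 = 0.41. In the third row the pooled T01−TAU difference averages 0.55 against a true 0.40. New subjects alone are unbiased.

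**Over-run.** Section 3.7.4.2 lets enrolled subjects finish, so the second cohort can exceed 33 per arm. With 66 new per arm (an assumed size), the pooled T01 vs S01 test passes in about 20% (no effect) or 18% (equal games), and the null estimate falls to about 0.20 SD. With 100 new per arm the figures are 15%, 14% and 0.15 SD.

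**Unconditional size.** A false pooled T01 over S01 result reached by this path: 0.46% × 0.29 = 0.13% of trials with no effect; 2.05% × 0.26 = 0.5% with equal games. With all arms equal, T01 vs TAU type I error is 1.74% against 1.67% without an interim. The chance of any false positive at a fixed 0.0167 is 4.57% against 4.48%.

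**Power of a separate replication.** With 33 per arm, d = 0.40 and one-tailed 0.0167, power is about 30% per contrast. For both contrasts at d = 0.40 with MEL-S01 equal to TAU, it is 16% (21% with Holm). 80% power per contrast would need 112 per arm.

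**The case against.** Three stronger readings are tempting, and the documents do not support them.

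- **That the plan prescribes pooling.** It does not. Sections 3.7.2 and 3.7.3 merely fail to exclude the interim subjects, and the words in 3.7.5.1 about the next 33 and a replication cohort could mean a separate look at new subjects. Pooling is the default because no other analysis is defined, so it would be too much to say outright that the safeguard fails.
- **That about a quarter of chance interim findings would be corroborated, as a general rate.** The 26–29% is for one contrast at exactly 33+33. The interim finding concerns two contrasts, and with no device effect both pass at 0.0167 only 14% of the time. Over-run lowers the rates further.
- **That the trial's error rate is materially inflated.** These are conditional probabilities on a path that is rare under the null, and overall type I error is almost unchanged. At the larger effects, where the path is common, the consequence is mainly overestimation of a real difference.

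It is also fair to say that separating the cohorts is a weak test by itself, since 33 per arm would usually miss a true d = 0.40. That limits what a separate replication can show. It does not make the pooled result a replication.

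**Conclusion.** The point holds in this form: the replication cohort has no test, alpha, success criterion or analysis set, and the default analysis reuses the data that triggered it. If pooled at 33+33, chance confirmation is about 26–29% per contrast, or 14% for both contrasts with no device effect, against about 1.6% per contrast in new subjects. Estimates are biased upward: about 0.30 SD for a true 0, 0.41 for 0.20 and 0.53 for 0.40. What is damaged is the claim of corroboration and the reported effect size, not the overall type I error.

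The figures assume normal outcomes with equal SD, two-sample t-tests standing in for the mixed model of 3.7.3, and exactly 33 per arm at each stage unless stated. The change should be made: the path is uncommon under the null, but it leads to the trial's strongest claim.

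**What to change.** Add to 3.7.5.1 that, if the rule is met, corroboration is tested only in subjects who were not in the interim dataset, over-run subjects included. State the alpha and the success criterion: both MEL-T01 contrasts significant under the plan's one-tailed Holm procedure. Report estimates and confidence intervals from those subjects. Label any pooled estimate as selected on the interim result, or adjust it for bias. State that 33 new subjects per arm give about 30% power per contrast at d = 0.40, so a non-significant replication is inconclusive.

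An equally valid alternative is to remove the replication wording and pool openly, with a pre-specified sequential boundary and a bias-adjusted estimate.

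The cost of the first option is a few sentences and no extra subjects. The interval on this path widens: standard error √(2/33) = 0.25 SD against √(2/66) = 0.17 SD for the pooled set, and less so if over-run subjects enlarge the new cohort.
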